5.2.2.2. Additional Analysis

To assess the sensitivity of the results of the MMRM analysis of the primary endpoint, an analysis of covariance (ANCOVA) model for the change from baseline to the 12-week endpoint in LSAS total score will be carried out. The ANCOVA model will include factors for treatment, country and presence of comorbid MDD and baseline LSAS total score and age as a covariate. In addition, the same ANCOVA model will also be performed on observed case data at Week 12.

As a secondary analysis, the MMRM model described in [Section 5.2.2.1](#) will be fitted with race, history of MDD and baseline SDS total score as additional covariates.

As a sensitivity analysis, the MMRM model described in [Section 5.2.2.1](#) will be fitted on the set of ITT subjects excluding the subjects who had completed the study at the time it was suspended (9 subjects in each treatment group).

5.3. Secondary Efficacy Endpoints

5.3.1. Definitions

5.3.1.1. LSAS fear/anxiety subscale

The LSAS fear/anxiety subscale will be calculated by summing the 24 fear/anxiety item scores of the LSAS, and ranges from 0 to 72.

5.3.1.2. LSAS avoidance subscale

The LSAS avoidance subscale will be calculated by summing the 24 avoidance item scores of the LSAS, and ranges from 0 to 72.

5.3.1.3. LSAS $\geq 50\%$ improvement from baseline on total score

The percentage change from baseline is calculated as

$$100 * \frac{(LSAS \text{ total score at any time point} - LSAS \text{ total score at baseline})}{LSAS \text{ total score at baseline}}$$

A $\geq 50\%$ improvement on LSAS total score means that the percentage change from baseline is ≤ -50 in this calculation.

5.3.1.4. LSAS $\geq 30\%$ improvement from baseline on total score

The percentage change from baseline is calculated as

$$100 * \frac{(LSAS \text{ total score at any time point} - LSAS \text{ total score at baseline})}{LSAS \text{ total score at baseline}}$$

A $\geq 30\%$ improvement on LSAS total score means that the percentage change from baseline is ≤ -30 in this calculation.

5.3.1.5. Structured Interview Guide for the Hamilton Anxiety scale (SIGH-A) total score

The SIGH-A is included as a means to determine the frequency and severity of signs and symptoms of anxiety, including subjects with comorbid GAD and MDD, and determine both their influence on treatment and their responsiveness to treatment.

The original HAM-A scale assesses the severity of different anxiety-related symptoms (Hamilton 1959⁴; Hamilton 1969³). As the original HAM-A lacks instructions for administration and clear anchor points for the assignment of severity ratings, the structured interview guide version will be used in the current study (Shear 2001)⁹. The SIGH-A has been shown to have high inter-rater and test-retest reliability and produced similar but consistently higher (+ 4.2) scores compared to the original HAM-A. Correlation with a self-report measure of overall anxiety has also been shown to be high (Shear 2001)⁹. Subscales, such as the HAM-A₆ which focuses on psychic anxiety and may be more sensitive to certain treatments, can be derived from the SIGH-A.

The SIGH-A scale consists of 14 items with a score of 0 to 4. Higher scores indicate higher severity (0-absent, 1-mild, 2-moderate, 3-severe, 4-incapacitating). The SIGH-A total score will be calculated by summing the 14 item scores, and ranges from 0 to 56. Higher scores indicate worse results.

5.3.1.6. HAM-A₆ score

The HAM-A₆ is a 6-item subscale derived from the original Hamilton Anxiety scale (HAM-A). It comprises five psychic anxiety symptoms: anxious mood, psychic tension, fears, intellectual disturbances, and anxious behavior observed at the interview, as well as one somatic item, muscular tension. The HAM-A₆ score will be calculated by summing the 6 item scores, and ranges from 0 to 24. Higher scores indicate greater severity of symptoms.

5.3.1.7. HDRS₁₇ total score

The HDRS₁₇ is a clinician-administered rating scale designed to assess the severity of symptoms in subjects diagnosed with depression (Hamilton M 1960)². It is the most widely

used symptom severity measure for depression. Each of the 17 items is rated by the clinician on either a 3- or a 5-point scale.

The HDRS₁₇ total score will be calculated by summing the 17 item scores, and ranges from 0 to 52. Higher scores indicate greater severity of depression.

The original HDRS₁₇ scale lacks instructions for administration and clear anchor points for the assignment of severity ratings. For this reason, the structured interview guide version of the HDRS₁₇ (the Structured Interview Guide for the Hamilton Depression Scale [SIGH-D]) will be used in the current study to facilitate and standardize gathering clinical information from the subject.

5.3.1.8. HDRS₁₇ anxiety/somatization factor score

The HDRS₁₇ anxiety/somatization factor derived from Cleary and Guy's factor analysis of the HDRS₁₇ scale, includes six items from the original 17-item version: the items for psychic anxiety, somatic anxiety, gastrointestinal somatic symptoms, general somatic symptoms, hypochondriasis, and insight. The HDRS₁₇ anxiety/somatization factor will be calculated as the sum of the 6 item scores, and ranges from 0 to 18, with higher scores indicating greater severity of symptoms.

5.3.1.9. HAM-D₆ score

A 6-item subscale from the HDRS₁₇ (HAM-D₆) will be analyzed as it has been shown to be a uni-dimensional scale that provides information to core depressive symptoms and is sensitive to treatment response (Bech 1975)¹. The six items are: depressed mood, guilt feelings, work and interests, psychomotor retardation, psychic anxiety, and general somatics (tiredness and pains). The HAM-D₆ score will be calculated by summing the 6 items scores, and ranges from 0 to 22. Higher scores indicate greater severity of core symptoms.

5.3.1.10. CGI-I

The clinical global impression – improvement (CGI-I) is a 7-point scale that requires the clinician to assess how much the subject's illness has improved or worsened relative to a baseline state at the beginning of the intervention. The CGI-I is rated as: 1=very much improved; 2=much improved; 3=minimally improved; 4=no change; 5=minimally worse; 6=much worse; 7=very much worse.

Responders on the CGI-I are defined as subjects with a score of 1=very much improved or 2=much improved.

5.3.1.11. SIGH-A ≥50% improvement from baseline on total score

The percentage change from baseline is calculated as

$$100 * \frac{(\text{SIGH A total score at any time point} - \text{SIGH A total score at baseline})}{\text{SIGH A total score at baseline}}$$

A ≥50% improvement on SIGH-A total score means that the percentage change from baseline is ≤ -50 in this calculation.

5.3.2. Analysis Methods

For all continuous secondary endpoints, descriptive statistics of actual values and changes from baseline at each scheduled time point and endpoint will be provided by treatment group (mean, SD, median and range). This includes LSAS fear/anxiety subscale, LSAS avoidance subscale, SIGH-A total score, HAM-A₆ score, HDRS₁₇ total score, HDRS₁₇ anxiety/somatization factor score and HAM-D₆ score. A mean-SE plot over time will be presented for these continuous endpoint observed values by treatment group.

For each of the continuous secondary endpoints, the JNJ-42165279 treatment group will be compared to placebo by means of a mixed-effects model using repeated measures (MMRM) with time, treatment (placebo, JNJ-42165279) and time-by-treatment interaction as factors, baseline score of the continuous endpoint and age as a continuous covariate and country and presence of comorbid MDD as categorical covariates. An unstructured variance-covariance matrix will be used. In case of convergence problems, simpler variance-covariance structures such as Toeplitz or AR(1) will be considered. The selection of any of these structures will be determined after exploration of the observed correlation structure. The treatment-placebo differences will be obtained using the appropriate contrast in the MMRM model at the 12-week endpoint. One-sided p-values with level of significance of 20% will be derived as described in Section 5.2.2.1.

Frequency counts and percentages will be provided at each scheduled time point and endpoint by treatment group for the following variables: LSAS $\geq 50\%$ improvement, LSAS $\geq 30\%$ improvement, CGI-I, CGI-I response and SIGH-A $\geq 50\%$ improvement.

5.4. Exploratory Efficacy Endpoints

5.4.1. Definition

5.4.1.1. SDS

The Sheehan Disability Scale (SDS) is a composite of three self-rated items designed to measure the extent to which three major sectors in the patient's life are impaired by panic, anxiety, phobic, or depressive symptoms. This anchored visual analog scale uses visual-spatial, numeric, and verbal descriptive anchors simultaneously to assess disability across three domains: work, social life, and family life. An SDS total score will be calculated as the sum of the three self-rated item scores, and ranges from 0 to 30. Higher scores indicate higher impairment of the patient's life.

5.4.1.2. GAD-7

Generalized Anxiety Disorder 7 (GAD-7) is a self-reported questionnaire for screening and severity measuring of generalized anxiety disorder (GAD) and is of particular interest because of the frequent comorbidity of GAD with SAD. GAD-7 has seven items, which measure severity of various signs of generalized anxiety disorder according to reported response categories of "not at all," "several days," "more than half the days," and "nearly every day." A GAD-7 total score is calculated as the sum of the 7 item scores, and ranges from 0 to 21, with higher scores indicating higher severity of symptoms.

5.4.1.3. SHAPS

The Snaith-Hamilton Pleasure Scale (SHAPS) is a 14-item, self report instrument developed for the assessment of hedonic capacity. The SHAPS was developed to minimize cultural, gender, and age biases in the evaluation of hedonic capacity. It not only measures hedonic tone, but also its absence, i.e. anhedonia. Anhedonia can be a core symptom of depression. Four major domains are covered in the scale, namely interest/pastimes, social interaction, sensory experience, and food/drink. Each of the SHAPS items has a set of four response categories: Strongly Disagree, Disagree, Agree and Strongly Agree, with either of the Agree responses receiving a score of 0 and either of the Disagree responses receiving a score of 1. A SHAPS total score will be calculated as the sum of the 14 item scores, and ranges from 0 to 14. A higher SHAPS total score indicates higher levels of present state of anhedonia.

5.4.1.4. MOS Sleep – R

Symptoms of poor sleep commonly occur in anxiety and mood disorders. The Medical Outcomes Study Sleep-Revised (MOS Sleep-R) is a subject-completed scale containing 12 items that addresses various dimensions of sleep. Ten items are answered on a 6-point scale, where 1=“all of the time” and 6=“none of the time”. One item on sleep latency is answered on a 5 point Likert scale from 1=“0-15 minutes” to 5=“more than 60 minutes”. One item on the duration of sleep allows the subject to write in the number of hours slept per night.

The instrument yields six subscales: sleep disturbance, snoring, shortness of breath or headache, sleep adequacy, sleep somnolence, and sleep quantity. The version to be used in this study has a recall period of the 4 past weeks. Quantity of sleep is scored as the average number of hours slept per night. Other subscales scores are converted to a T-score with a mean of 50, standard deviation (SD) of 10 and range of 0 to 100, where higher scores indicate fewer sleep-related problems.

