# Medical Outcomes Study Sleep-Revised (MOS Sleep-R)

Symptoms of poor sleep commonly occur in anxiety and mood disorders. The Medical Outcomes Study Sleep-Revised (MOS Sleep-R) is a subject-completed scale containing 12 items that addresses various dimensions of sleep. The instrument yields six subscales: sleep disturbance, snoring, shortness of breath or headache, sleep adequacy, sleep somnolence, and sleep quantity. Most items are answered on 5-point Likert scales for 10 of the items, where 1="all of the time," and 5="none of the time," 1 item on sleep latency is answered on a 5 point Likert scale from 1="0-15 minutes" to 5="more than 60 minutes." The final item on the duration of sleep allows the subject to write in the number of hours slept per night. The version to be used in this study has a recall period of the 4 past weeks. Quantity of sleep is scored as the average number of hours slept per night. Other subscales scores are converted to a T-score with a mean of 50, standard deviation (SD) of 10 and range of 0 to 100, where higher scores indicate fewer sleep-related problems. The instrument has good data supporting its psychometric properties, and development history (Quick Start Guide for the MOS Sleep Scale-Revised 2010).

An example of the MOS Sleep-R is provided in Attachment 5.

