#### Exploratory

- The change from baseline to the 12-week endpoint for: SDS (Sheehan Disability Scale) GAD-7, Snaith-Hamilton Pleasure Scale (SHAPS) and MOS Sleep-R.
- The change from baseline to the 12-week endpoint for Quality of Life Enjoyment and Satisfaction Questionnaire (Q-LES-Q)
- Self-Assessment of Treatment Experience scale
- The change from baseline to the 12-week endpoint for: HDRS17 total score, HDRS17 anxiety/somatization factor total score and HAM-D6 score in subjects with comorbid MDD.
- The change from baseline to the 12-week endpoint for: SIGH-A total score and HAM-A6 score in subjects with comorbid GAD.
- The distribution (number and percentage) of subjects with comorbid MDD who are responders on depressive symptoms (based on two definitions: either  $\geq$ 50% or  $\geq$ 30% improvement on HDRS17 total score from baseline) at the 12-week endpoint.
- The distribution (number and percentage) of subjects with comorbid GAD who are responders on anxious symptoms (≥50% improvement on SIGH-A total score from baseline) at the 12-week endpoint.

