Attachment 5: Medical Outcomes Study (MOS) - 12-Item Sleep Scale Acute - Revised

# Your Sleep

For each of the following questions, please mark an  $\boxtimes$  in the one box that best describes your answer.

1. How long did it usually take for you to fall asleep during the past 4 weeks?

0-15 minutes	16-30 minutes	31-45 minutes	46-60 minutes	More than 60 minutes
•		$\bullet$		· _ ▼
1	2	□ 3 ▲		□,

2. On the average, how many hours did you sleep each night during the past 4 weeks?

Write in number of hours per night:

3. How often during the past 4 weeks did you...

		Most of the time	Some of the time	A little of the time	None of the time
a	feel that your sleep was not quiet	•	•	•	•
	(moving restlessly, feeling tense, speaking, etc., while sleeping)?	🔲 2	s		🗖 5
b	get enough sleep to feel rested upon waking in the morning?	🗌 2	] 3	4	5
ε	awaken short of breath or with a headache?	🔲 2	D 3	4	🗖 5
d	feel drowsy or sleepy during the day?		D 3	4	🗖 5
e	have trouble falling asleep?		3		🗖 5

Copyright, 1986, RAND. MOS 12-Item Sleep Scale – Revised 2010 United States (English) How often during the past 4 weeks did you...

		All of the time	Most of the time	Some of the time	A little of the time	None of the time
,	awaken during your sleep time and have trouble falling asleep again?	▼ □ 1	•	• • • • • • • • • • • • • • • • • • • •	• 	▼ 5
g	have trouble staying awake during the day?	🗖 1	🔲 2	B 3		5
h	snore during your sleep?	D 1	🗋 2			5
ı	take naps (5 minutes or longer) during the day?	🗖 1	🗖 2			5
ı	get the amount of sleep you needed?	🗖 1			,⊡•	5
	SR		2			

Copyright, 1996, RAND. MOS 12-Item Sleep Scale – Revised 2010 United States (English)

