5.4.2. Analysis Methods

For all continuous exploratory endpoints, descriptive statistics of actual values and changes from baseline at each scheduled time point and endpoint will be provided by treatment group (mean, SD, median and range). A mean-SE plot over time will be presented for the observed values by treatment group. This includes SDS total score, GAD total score, SHAPS total score, MOS Sleep-R, Q-LES-Q percentage maximum possible score, HDRS₁₇ total score, HDRS₁₇ anxiety/somatization factor score, HAM-D₆ score, SIGH-A total score and HAM-A₆ score.

Frequency counts and percentages will be provided at each scheduled time point and endpoint by treatment group for the following variables: Q-LES-Q last 2 items, Self-Assessment of Treatment Experience scale, HDRS₁₇ $\geq 50\%$ improvement, HDRS₁₇ $\geq 30\%$ improvement and SIGH-A $\geq 50\%$ improvement.

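### The SAP codes ten MOS Sleep-R items on six points, but the protocol and the attached form have five; scoring that takes its item codes from the SAP would mis-scale the subscales using those items

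*SAP*

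**What the plan says.** SAP section 5.4.1.4 describes the MOS Sleep-R as 12 items: "Ten items are answered on a 6-point scale", anchored at 1 for all of the time and 6 for none of the time; "One item on sleep latency is answered on a 5 point Likert scale"; and one item asks for hours slept. For scoring, sleep quantity stays in hours, and "Other subscales scores are converted to a T-score with a mean of 50", an SD of 10 and a range of 0 to 100, higher scores meaning fewer sleep problems.

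Protocol section 3.2 describes the same instrument differently: "Most items are answered on 5-point Likert scales for 10 of the items", with 5 as the code for none of the time. Attachment 5 of the protocol reproduces the form, labelled as the 2010 revision. Its final response column is headed "None of the time" and its box is coded 5.

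Protocol section 9.3.2 lists the measure under exploratory endpoints: "The change from baseline to the 12-week endpoint for: SDS (Sheehan Disability Scale) GAD-7, Snaith-Hamilton Pleasure Scale (SHAPS) and MOS Sleep-R". SAP section 5.4.2 sets the analysis: "For all continuous exploratory endpoints, descriptive statistics of actual values and changes from baseline", together with a mean-SE plot by treatment group. No model or test is planned for it.

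**The concern.** SAP section 5.4.1 is where the exploratory scales are defined for analysis, so a programmer would look there for item codes. For the neighbouring scales it gives workable scoring: a 0–21 sum for the GAD-7, 0/1 item coding for the SHAPS, and an explicit formula with minimum and maximum raw scores for the Q-LES-Q. For the MOS Sleep-R, the response codes are almost the only item-level numbers given, and for ten of the twelve items the top code is one that the attached form does not offer.

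The number of categories matters because the items do not all point the same way. Answering all of the time is favourable for the items on feeling rested and on getting the sleep needed (3b and 3j), and unfavourable for items such as restless sleep or trouble falling asleep (3a and 3e). Since higher scores must mean fewer problems, some items have to be reversed, and the reversal constant depends on the top code. At stake are the MOS Sleep-R summary values, changes from baseline and plots.

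**Working it through.** **1. Counting the categories**

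| Source | Ten frequency items | Code for none of the time | Latency item |
|---|---|---|---|
| SAP 5.4.1.4 | 6-point | 6 | 5-point |
| Protocol 3.2 | 5-point | 5 | 5-point |
| Protocol Attachment 5 | 5 columns (all, most, some, a little, none) | 5 | 5 boxes |

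The form has one latency item, one hours item and ten frequency items (3a to 3j): 1 + 1 + 10 = 12, as both documents say. The extracted text loses one column header above 3a–3e, but the last box there is also coded 5, and 3f–3j show all five headers. The SAP's 6 therefore does not reproduce; the protocol's 5 does. In the SAP the 6 appears both as the number of points and as the top anchor, so it is unlikely to be a one-character extraction fault. The amendments listed in the protocol do not touch this scale. The two texts otherwise agree on the latency item, the six subscales, the four-week recall and the T-scores.

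**2. What reversal alone would do**

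Correct reversal on codes 1–5 is 6 − x. Under the SAP's coding it is 7 − x, which equals (6 − x) + 1. Each reversed item would sit one raw point too high. The change from baseline would be unaffected:

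(7 − x₂) − (7 − x₁) = x₁ − x₂ = (6 − x₂) − (6 − x₁).

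**3. What rescaling could do (illustration only)**

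Neither document gives an item rescaling. Assume a linear 0–100 rule with k categories: 100(x − 1)/(k − 1) for forward items and 100(k − x)/(k − 1) for reversed items. Data collected on the form take x = 1 to 5.

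| x | Forward, k = 5 | Forward, k = 6 | Reversed, k = 5 | Reversed, k = 6 |
|---|---|---|---|---|
| 1 | 0 | 0 | 100 | 100 |
| 2 | 25 | 20 | 75 | 80 |
| 3 | 50 | 40 | 50 | 60 |
| 4 | 75 | 60 | 25 | 40 |
| 5 | 100 | 80 | 0 | 20 |

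A one-category change is worth 100/4 = 25 points with the correct key and 100/5 = 20 with the six-point key, a ratio of 0.8. This applies to the ten frequency items only. Sleep quantity is in hours, and the latency item is five-point in every source.

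**4. Whether this reaches the T-score**

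The SAP does not say whether T-scores are standardised to external norms or to the trial sample. If to the sample, a factor common to all items of a subscale would cancel; if to external norms, it might not. In a subscale that combined the latency item with frequency items, the shrinkage would not be uniform. The documents give no item-to-subscale map, so this cannot be settled.

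**The case against.** The strongest reply is that the 6 is descriptive text. The SAP writes no computation that uses it: no reversal rule, no item-to-subscale map, no rescaling and no raw-to-T conversion. Nobody could score the subscales from section 5.4.1.4 alone, so an outside key is needed. Protocol section 3.2 mentions a guide to the 2010 revised scale, and the attached form is that revision. Responses are collected on a form offering only 1 to 5, so no data are affected, and a six-point key might be noticed because no 6 would ever appear. Any mis-scaling would apply alike to both arms, in an endpoint that is neither tested nor used for a decision.

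Most of this stands, and it rules out the stronger readings a reader might infer:

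- *That scores computed from the SAP are wrong.* This is not shown, because the SAP contains no computation in which the 6 is used.
- *That every change from baseline is understated by 20%.* That needs the assumed linear rule. A reversal error alone leaves change intact, and the hours and latency items are outside the problem.
- *That the stated 0–100 range cannot be reached.* The documents attach that range to the T-score and do not link it to any item rescaling.

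What the reply does not remove is the contradiction itself. The SAP names no scoring source for this scale, and the item codes it does give conflict with the form.

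**Conclusion.** The SAP's item coding for ten of the twelve MOS Sleep-R items is wrong as written, judged against both the protocol text and the form. That much is certain. The consequence is a scoring risk, not a demonstrated error. Its size runs from zero, if the revised form's own key is applied, to an amount the documents do not fix; the drop from 25 to 20 points per category is one scenario under an assumed linear rule.

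Severity is low. Only exploratory, descriptive output could be affected, and the LSAS analysis, its significance level, the power and the sample size do not depend on this scale. The point is still worth correcting, because some items must be reversed and the correct reversal depends on the number of categories.

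**What to change.** In SAP section 5.4.1.4, describe the ten items as five-point, with 1 for all of the time and 5 for none of the time. Add a sentence stating that reverse coding, the item-to-subscale map and the T-score conversion follow the scoring key of the five-point revised form in protocol Attachment 5. Check that the scoring program uses 5 as the item maximum.

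The cost is one or two sentences and a program check. Data collection and the other planned analyses do not change, and the correction has no downside.
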